2.5 Dosing Rationale

In this trial, DFMO will be dosed orally. The bioavailability of orally administered DFMO ranges from 50-60% in multiple studies.²⁶ The dose of DFMO to be used for this trial (6,750 mg/m²/day divided 3 times a day orally) was the recommended phase 2 dose determined on the NANT consortium N2012-01 trial of DFMO in combination with cyclophosphamide, topotecan and celecoxib. The half-life of DFMO is 3-4 hours when delivered orally, therefore, a TID dosing regimen provides continuously higher plasma concentrations to optimize systemic polyamine depletion. DFMO will be given at this dose during therapy.

Starting with Amendment 2A, DFMO will be given on a discontinuous basis, allowing for a 7-day break without DFMO administration in each cycle, similar to the dosing used in the NANT N2012-01 trial. Four of the first eight patients enrolled on the DFMO containing arm (Regimen B) of this study with available ototoxicity data developed documented Grade 3 hearing loss from their baseline. Hearing loss is a known toxicity of DFMO and is typically reversible. Prior studies have shown that the risk of DFMO-associated ototoxicity is decreased when the DFMO is administered in an intermittent fashion, with a 7-14 day break per cycle. At similar or higher dosing compared to that used in ANBL1821, the incidence of Grade 3 or higher hearing loss with interrupted dosing was less than 5%^{40, 30, 29} Similarly, in the NANT2012-01 trial, DFMO dosed at 3000-9000 mg/m²/day for 21 days out of a 28-day cycle resulted in only 1 of 24 patients experiencing new Grade 3 hearing loss. This hearing loss was reversible and did not recur with re-treatment.³⁹ The NANT2012-01 trial was conducted in a relapsed NBL population similar to that of ANBL1821 supporting that intermittent dosing of

DFMO may decrease the risk for significant ototoxicity. Therefore, given the incidence of hearing loss seen initially on this study with continuous dosing, this trial will now include a 7-day break in DFMO dosing to decrease the chances of additional hearing loss. Additionally, DFMO will be held at first detection of significant hearing loss.

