4.5.2 Required Observations in Regimen A Cycle 2 and Subsequent Cycles

- a. History, physical exam with vital signs, performance status
- b. Height, weight, BSA
- c. CBC with differential and platelets. Patients who experience Grade 4 neutropenia should have CBCs checked at least twice per week until recovery to Grade 3. If patients remain on study for > 4 cycles and cytopenias are not observed, CBCs should be obtained at the start of subsequent cycles and as clinically indicated.
- d. Electrolytes, BUN, creatinine, calcium, magnesium, phosphorus, albumin
- e. ALT, total bilirubin
- f. Audiogram or BAER (use same mode of testing as baseline). Obtain at the end of Cycle 2 and Cycle 6.
- g. Bilateral bone marrow aspirates and biopsies. Obtain at the end of Cycles 2, 4, 6, and every fourth cycle[&] thereafter for patients with bone marrow involvement at baseline (study enrollment) or patients with *any* prior history of bone marrow involvement. Obtain at the end of Cycles 2 and 6 for *all* patients, including those without bone marrow involvement at baseline (study enrollment) and those without *any* prior history of bone marrow involvement.*
- h. Cross sectional tumor imaging of original primary site and any non-osseous sites of disease involvement at study entry (MRI or CT) (submit for central review as soon as scan is obtained after Cycles 2, 4, and 6). Obtain at the end of Cycles 2, 4, 6, and every fourth cycle[&] thereafter. Patients with no measurable or non-measurable soft tissue disease (i.e., MIBG avid bone lesions or bone marrow involvement only) at baseline are only required to obtain appropriate cross-sectional imaging (CT and/or MRI) at baseline and at the end of Cycles 2 and 6 (see [Section 15.1](#) for imaging details).*
- i. ¹²³I-MIBG scan (submit for central review as soon as scan is obtained after Cycles 2, 4, and 6). Obtain at the end of Cycles 2, 4, 6, and every fourth cycle[&] thereafter.*
- j. Curie score profile (patients with MIBG avid disease; see [Appendix IX](#) for worksheet) (submit for central review as soon as scan is obtained after Cycles 2, 4, and 6). Obtain at the end of Cycles 2, 4, 6, and every fourth cycle[&] thereafter.
- k. FDG-PET scan for patients with ¹²³I-MIBG non-avid disease (submit for central review as soon as scan is obtained after Cycles 2, 4, and 6). Obtain at the end of Cycles 2, 4, 6, and every fourth cycle[&] thereafter.*

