4.7.2 Required Observations in Regimen B Cycle 2 and Subsequent Cycles

- a. History, physical exam with vital signs, performance status
- b. Height, weight, BSA
- c. CBC with differential and platelets (patients who experience Grade 4 neutropenia should have CBCs checked at least twice per week until recovery to Grade 3). If patients remain on study for > 4 cycles and cytopenias are not observed, CBCs should be obtained at the start of subsequent cycles and as clinically indicated
- d. Electrolytes, BUN, creatinine, magnesium, phosphorus, albumin
- e. ALT, total bilirubin
- f. Audiogram or BAER (use same mode of testing as baseline). Obtain at the end of Cycle 2 and end of every 2nd cycle thereafter.
- g. Bilateral bone marrow aspirates and biopsies. Obtain at the end of Cycles 2, 4, 6, and every fourth cycle[&] thereafter for patients with bone marrow involvement at baseline (study enrollment) or patients with *any* prior history of bone marrow involvement. Obtain at the end of Cycles 2 and 6 for all patients, including those without bone marrow involvement at baseline (study enrollment) and those without *any* prior history of bone marrow involvement.*
- h. Cross sectional tumor imaging of original primary site and any non-osseous sites of disease involvement at study entry (MRI or CT) (submit for central review as soon as scan is obtained after Cycles 2, 4, and 6). Obtain at the end of Cycles 2, 4, 6, and every fourth cycle[&] thereafter. Patients with no measurable or non-measurable soft tissue disease (i.e., MIBG avid bone lesions or bone marrow involvement only) at baseline are only required to obtain appropriate cross-sectional imaging (CT and/or MRI) at baseline and at the end of Cycles 2 and 6 (see [Section 15.1](#) for imaging details).*
- i. ¹²³I-MIBG scan (submit for central review as soon as scan is obtained after Cycles 2, 4, and 6). Obtain at the end of Cycles 2, 4, 6, and every fourth cycle[&] thereafter.*
- j. Curie score profile (patients with MIBG avid disease; see [Appendix IX](#) for worksheet) (submit for central review as soon as scan is obtained after Cycles 2, 4, and 6). Obtain at the end of Cycles 2, 4, 6, and every fourth cycle[&] thereafter.
- k. FDG-PET scan for patients with ¹²³I-MIBG non-avid disease (submit for central review as soon as scan is obtained after Cycles 2, 4, and 6). Obtain at the end of Cycles 2, 4, 6, and every fourth cycle[&] thereafter.*

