To assess exploratory aim [1.3.3](#), the occurrence of pain on each regimen as reported by patient report and opiate use will be descriptively summarized. Descriptive and summary statistics will be used to describe the scores from the Faces Pain Scale-Revised during the dinutuximab infusion and on Day 1 with irinotecan and temozolomide alone for each arm separately. Confidence intervals will be constructed for the mean and frequency estimates. The Day 1 patient reported outcome data are expected to be similar between the 2 regimens, while differences during or after completion of treatment may be observed.

9.4 **Evaluability for Response**

All eligible patients will be considered evaluable for response.

9.5 **Evaluability for Toxicity**

All eligible patients will be evaluable for toxicity from the time of their first treatment with eflornithine, irinotecan, temozolomide, or dinutuximab.

The study committee will review ototoxicity data closely during monthly committee meetings. If a difference in the incidence of hearing loss of $>15\%$ in eligible patients treated on the interrupted schedule enacted with Amendment 2A is detected among patients on the DFMO-containing Regimen B as compared to Regimen A, the study committee will notify the DSMC and CTEP and discuss potentially suspending accrual and further modifying the DFMO dose and/or schedule. In this context, hearing loss is defined as “an increase of 15dB or more from baseline in hearing threshold at two contiguous frequencies between 500-3000Hz” as this is the criterion for which DFMO is held for hearing loss.

9.6 **Gender and Minority Accrual Estimates**

The gender and minority distribution of the study population is expected to be:

DOMESTIC PLANNED ENROLLMENT REPORT								
Racial Categories	Ethnic Categories						Total	
	Not Hispanic or Latino		Hispanic or Latino					
	Female	Male	Female	Male				

American Indian/ Alaska Native	0	0	0	0	0
Asian	0	3	0	0	3
Native Hawaiian or Other Pacific Islander	0	0	0	0	0
Black or African American	8	5	0	0	13
White	18	29	5	10	62
More Than One Race	0	0	0	0	0
Total	26	37	5	10	78

INTERNATIONAL (including Canadian participants) PLANNED ENROLLMENT REPORT						
Racial Categories	Ethnic Categories				Total	
	Not Hispanic or Latino		Hispanic or Latino			
	Female	Male	Female	Male		
American Indian/ Alaska Native	0	0	0	0	0	
Asian	0	2	0	0	2	
Native Hawaiian or Other Pacific Islander	1	1	0	0	2	
Black or African American	0	0	0	0	0	
White	4	7	2	0	13	

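### The Section 9.5 hearing-loss trigger compares regimens tested on different audiogram schedules, so part of any excess on Regimen B can come from more frequent testing

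*Combined protocol and SAP*

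**What the plan says.** **Schedules.** Section 4.5.2, item f, for Regimen A audiograms: "Obtain at the end of Cycle 2 and Cycle 6". Section 4.7.2, item f, for Regimen B: "Obtain at the end of Cycle 2 and end of every 2nd cycle thereafter". Section 7.1 adds end-of-therapy and 12-month audiograms for both regimens. Its footnote 3 moves the end-of-therapy test to about 30 days later if the patient was tested in the preceding 28 days.

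**Trigger.** Section 9.5: "The study committee will review ototoxicity data closely during monthly committee meetings". A difference in incidence above 15%, "detected among patients on the DFMO-containing Regimen B as compared to Regimen A", among eligible patients on the interrupted schedule of Amendment 2A, means that "the study committee will notify the DSMC and CTEP and discuss potentially suspending accrual" as well as further changes to DFMO. An event is "an increase of 15dB or more from baseline in hearing threshold at two contiguous frequencies between 500-3000Hz". Section 9.5 does not name the audiograms that count, adjust for the number of tests, or ask for a confirmatory test.

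**Background.** Section 2.5: "Hearing loss is a known toxicity of DFMO and is typically reversible". Section 4.1 allows up to 17 cycles for patients enrolled before Amendment 4 who keep a minor response or better, and at most 6 cycles for later enrollees.

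**The concern.** Incidence from periodic testing depends on how often one looks. By the end of Cycle 6, Regimen A has had two on-treatment tests (Cycles 2 and 6) and Regimen B three (Cycles 2, 4 and 6). With 17 cycles the counts are two and eight. Three mechanisms follow, and all of them enlarge the B minus A difference:

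- A transient loss present only around Cycle 4 has a scheduled test on B and none on A.
- Test-retest shifts, and losses from other ototoxic drugs (Section 4.2.4 asks only that these be avoided when possible), are looked for more often on B.
- At a monthly look, even a permanent loss arising in Cycles 3–4 counts on B after Cycle 4. On A it usually waits until after Cycle 6, two 21-day cycles later.

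The trigger is meant to show whether DFMO on the interrupted schedule still causes excess hearing loss. If it is crossed partly because of the testing schedule, accrual and the DFMO regimen would be discussed on a figure whose bias Section 9.5 does not mention.

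**Working it through.** **Plan's own figure.** The documents give no derivation or operating characteristics for the 15% trigger, so there is nothing to reproduce there. I read it as 15 percentage points. The eventual denominators come from Section 9.3.1.1: 40% vs 60% response, one-sided 20% type I error, 80% power and continuity correction give 45 per arm, as stated.

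**Inputs.** On-treatment tests k: Regimen A 2; Regimen B 3 over six cycles, or 8 (Cycles 2, 4, …, 16) over 17 cycles. Let f be the chance that a single audiogram meets the 15 dB criterion for reasons other than DFMO. The documents do not give f; I assume 1–10%, the same in both arms, with independent tests.

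**Formulas.** Expected cumulative incidence = 1 − (1 − f)^k. Schedule-only excess = (1 − f)^2 − (1 − f)^k, where k is the number of tests on B. Example at f = 5%, six cycles: 14.3% − 9.8% = 4.5 points.

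| f | A, 2 tests | B, 3 tests | Excess, 6 cycles | B, 8 tests | Excess, 17 cycles |
|---|---|---|---|---|---|
| 1% | 2.0% | 3.0% | 1.0 | 7.7% | 5.7 |
| 2% | 4.0% | 5.9% | 1.9 | 14.9% | 11.0 |
| 3% | 5.9% | 8.7% | 2.8 | 21.6% | 15.7 |
| 5% | 9.8% | 14.3% | 4.5 | 33.7% | 23.9 |
| 10% | 19.0% | 27.1% | 8.1 | 57.0% | 38.0 |

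**Can six cycles alone reach 15 points?** The excess is f(1 − f)^2, which peaks at f = 1/3 with (1/3)(4/9) = 14.8 points. So it cannot, at any f.

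**Can it carry a smaller real difference over?** Take f = 10% and a DFMO effect that adds a 10% chance of loss. On two matched tests, B = 1 − 0.90 × 0.90^2 = 27.1% against A = 19.0%, a difference of 8.1 points. With B on three tests, 1 − 0.90 × 0.90^3 = 34.4%, a difference of 15.4 points.

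**Can it carry a chance difference over?** Exact binomial probability that observed B minus A exceeds 15 points at a single look, 30 per arm, no DFMO effect:

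| f | Equal schedules (2 vs 2) | As scheduled (2 vs 3) |
|---|---|---|
| 1% | 0.02% | 0.1% |
| 2% | 0.2% | 1.2% |
| 3% | 0.8% | 3.6% |
| 5% | 2.5% | 10.4% |
| 10% | 6.8% | 26.1% |

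These are single-look figures; the committee looks monthly.

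**Longer treatment.** If every patient completed 17 cycles, the expected excess would pass 15 points once f reaches about 2.8%. In a mixture of 6-cycle and 17-cycle patients, the share w needed at 17 cycles solves (1 − w) × (6-cycle excess) + w × (17-cycle excess) = 15. It is about 94% at f = 3%, 54% at 5% and 23% at 10%; at 2% no share suffices. With 20% at 17 cycles the excess is 5.4 points at 3%, 8.4 at 5% and 14.1 at 10%.

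**Counting an end-of-therapy audiogram in both arms** changes little: 3 vs 4 tests gives 4.3 points at f = 5% and 7.3 at 10%; 3 vs 9 gives 15.2 at 3%.

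**The case against.** **The size rests on assumptions.** This stands. The per-test rate is not in the documents, and at 1–2% the effect on the trigger is negligible for six-cycle patients. Tests within a child are correlated, so independence overstates the excess.

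**The trigger errs toward safety and only prompts discussion.** This also stands. It is not an automatic stop, and closer testing of the DFMO arm is reasonable because Section 5.2.7.1 uses the audiogram for individual holds. But nothing in Section 9.5 tells the committee that part of the difference may come from the schedule.

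**Transient loss is the toxicity being monitored.** Section 2.5 reports Grade 3 loss in four of the first eight Regimen B patients with data and calls such loss typically reversible. A loss found after Cycle 4 leads, under Section 5.2.7.1, to a hold for the rest of that cycle and one further full cycle. Hearing may then have recovered by the Cycle 6 test. A reader might infer that the trigger should be recomputed on shared time points alone. The documents do not support that, because genuine DFMO losses could leave the count.

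**The end-of-therapy audiogram could serve as a shared time point.** It cannot. Under footnote 3 of Section 7.1, a patient stopping after Cycle 4 would normally be tested at end of therapy on Regimen A, but about 30 days later on Regimen B because of the Cycle 4 test. Using it as matched would favour Regimen B.

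**Conclusion.** The concern holds as a limited bias in a safety comparison. The unequal schedules are explicit, Section 9.5 does not correct for them, and the bias enlarges the B minus A difference.

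Over six cycles, with an assumed 1–10% per test and independent tests, the schedule-only excess is about 1–8 points. At 30 per arm, the single-look chance of exceeding 15 points with no DFMO effect rises from about 0–7% to 0.1–26%. These are upper-end illustrations.

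A reader might infer that more frequent testing by itself pushes the trigger past 15%. For six-cycle patients that is wrong: the expected excess stays below 15 at any rate, and a real or chance difference must supply the rest. A larger excess arises only for patients enrolled before Amendment 4 who are treated beyond Cycle 6. It passes 15 points at a rate near 3% only if nearly all complete 17 cycles. At higher assumed rates a smaller share is enough (about half at 5%). Reaching 17 cycles requires a maintained minor response or better, and the trigger covers only patients on the Amendment 2A schedule. The documents do not say how many patients meet both conditions.

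**What to change.** In Section 9.5:

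1. Keep the difference based on all audiograms as the safety trigger for notifying the DSMC and CTEP.
2. Require a second difference to be reported with it, computed only on audiograms scheduled in both regimens (end of Cycle 2 and end of Cycle 6), with the denominator stated.
3. Tabulate losses by regimen and time point, so that those seen only at the additional Regimen B tests are visible.
4. State that both figures are considered before any decision on accrual or DFMO.
5. Do not treat the end-of-therapy audiogram as a matched time point.

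No new audiograms are needed, and individual management under Section 5.2.7.1 is unaffected. The cost is a sentence or two of protocol text and one more row in the monthly table. The matched figure understates reversible DFMO losses that recover during a hold, so it must supplement the trigger and not replace it.

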4.5.5 Additional guidance

- Capillary leak syndrome is an expected side effect of dinutuximab therapy. Complications of capillary leak syndrome can be mitigated if euolemia is maintained. Close monitoring of heart rate and urine output is required, and fluids should be adjusted to compensate for third space losses. The routine use

of diuretics during Days 2-5 is contraindicated unless clinically required (i.e. pulmonary capillary leak with respiratory compromise). Use of furosemide should be avoided when feasible due to ototoxicity concerns.

- Corticosteroid therapy should be used only for life-threatening conditions (i.e. treatment of increased intracranial pressure in patients with CNS tumors, symptomatic bronchospasm, stridor unresponsive to other measures or life-threatening allergic reactions). Corticosteroids will impair the immune activation that is a critical part of the protocol therapy. **The use of steroids at any time during immunotherapy requires clear justification and documentation.**
- The use of IVIG is discouraged. IVIG should not be given within 2 weeks of starting dinutuximab treatment and 1 week after completing dinutuximab therapy.
- Cytokines or growth factors (G-CSF, Interferon, etc.) not included in the Treatment Plan are prohibited during immunotherapy.

4.6 **Regimen B Cycle 1**

4.6.1 Therapy Delivery Map –CYCLE 1 Cycle 1 lasts 4 weeks (28 days). This cycle includes a lead-in of 7 days of DFMO (Days -6 to 0) prior to 21 days of chemotherapy.	Patient COG ID number _____ DOB _____
---	--

Begin Cycle 2 on Day 22 of Cycle 1 or when peripheral counts recover with ANC \geq 750/ μ L and platelets \geq 75,000/ μ L (whichever occurs later). See [Section 5.0](#) for dose modifications. This TDM is on 3 pages.

DRUG	ROUTE	DOSAGE	DAYS	IMPORTANT NOTES
Eflornithine (DFMO) IND# 141913	PO or via NG or Gtube	2250 mg/m ² /dose x 3 doses/day See dosing table in Appendix XII	Days -6 to +7 and Days 15 - 21	Round doses to the nearest 500 mg (see dosing table in Appendix XII). Note: During Days 1-5, consider giving one of the 3 times daily eflornithine doses and temozolomide close together in order to minimize potential for emesis and redosing.
Temozolomide (TEMO)	PO or via NG or Gtube	For patients \geq 0.5 m ² : 100 mg/m ² /dose For patients < 0.5 m ² : 3.3 mg/kg/dose See dosing table in Appendix VI .	Days 1 - 5	Max dose = 200 mg Round doses to the nearest 5 mg when using capsules. Administer at least 1 hour prior to IRIN administration. Temozolomide is dosed based on body surface area for patients whose BSA is at least 0.5 m ² . For patients with BSA < 0.5 m ² , dosing is based on body weight (kg).
Irinopecan (IRIN)	IV over 90 minutes	50 mg/m ² /dose	Days 1 - 5	Administer at least 1 hour after temozolomide, see Section 4.6.3 .
Dinutuximab (DIN)	IV over 10 hours*	17.5 mg/m ² /dose	Days 2 - 5	* Infusion duration may be extended up to 20 hours if needed. Start immediately after completion of NS bolus and irinopecan infusions. See Section 4.6.3 for detailed administration guidelines, including premedications and monitoring.
Sargramostim (GM-CSF)	SubQ (preferred) or IV over 2 hours	250 mcg/m ² /dose	Days 6 - 12	See Section 4.6.3 for administration guidelines.

4.6.1 Therapy Delivery Map –CYCLE 1 Cycle 1 lasts 4 weeks (28 days). This cycle includes a lead-in of 7 days of DFMO (Days -6 to 0) prior to 21 days of chemotherapy.	Patient COG ID number DOB
---	------------------------------

Date Due	Date Given	Day	Ht	cm	Wt	kg	BSA	m ²	Studies
			DFMO mg	TEMO mg	IRIN mg	DIN mg	GM-CSF mcg		
Enter calculated dose above and actual dose administered below									
		-6	mg						a – o
		-5	mg						
		-4	mg						
		-3	mg						
		-2	mg						
		-1	mg						
		0	mg						
		1	mg	mg	mg				a, c, d, e, n, o
		2	mg	mg	mg	mg			d, o
		3	mg	mg	mg	mg			d, o
		4	mg	mg	mg	mg			d, o
		5	mg	mg	mg	mg			d, o
		6	mg				mcg	n	
		7	mg				mcg		
		8					mcg	c, d, e	
		9					mcg		
		10					mcg		
		11					mcg		
		12					mcg		
		13							
		14							
		15	mg					c, d, e	
		16	mg						
		17	mg						
		18	mg						
		19	mg						
		20	mg						
		21	mg						
		22	Begin Cycle 2 on Day 22 or when peripheral counts recover with ANC \geq 750/ μ L and platelets \geq 75,000/ μ L (whichever occurs later).						

See [Section 5.0](#) for Dose Modifications for Toxicities and the COG Member website for Supportive Care Guidelines.

4.6.2 Required Observations in Regimen B Cycle 1

Page 3 of 3

All baseline studies must be performed prior to starting protocol therapy unless otherwise indicated below.

- a. History, physical exam with vital signs, performance status*
- b. Height, weight, BSA*
- c. CBC with differential and platelets (patients who experience Grade 4 neutropenia should have CBCs checked at least twice per week until recovery to Grade 3)*
- d. Electrolytes, BUN, creatinine, calcium, magnesium, phosphorus, albumin*
- e. ALT, total bilirubin*
- f. Pregnancy test (obtain for females of childbearing potential)
- g. ECHO or MUGA
- h. Audiogram or BAER – May be obtained within 3 weeks prior to the start of protocol therapy.
- i. Bilateral bone marrow aspirates and biopsies
- j. Cross sectional tumor imaging of original primary site and any non-osseous sites of disease involvement at study entry (MRI or CT) (submit for central review as soon as scan is obtained; see [Section 15.1](#) for imaging details for patients without measurable disease)
- k. ¹²³I-MIBG scan (submit for central review as soon as scan is obtained)
- l. Curie score profile (patients with MIBG avid disease; see [Appendix IX](#) for worksheet) (submit for central review as soon as scan is obtained)
- m. FDG-PET scan for patients with ¹²³I-MIBG non-avid disease (submit for central review as soon as scan is obtained)
- n. Specimens for correlative studies. Post-dinutuximab specimens should be collected at a single time point between Day 6 and Day 9. See [Section 14](#) and [Appendix X](#) for details.
- o. Faces Pain Scale Revised – can be done anytime on Days -6 and 1 of therapy. On Days 2-5 of therapy, should be performed at least 4 hours after the dinutuximab infusion has begun. See [Section 14.1.3](#) for additional detail.

* These baseline studies must be repeated on Day -6 if not performed within 72 hours of Day -6.

This listing only includes evaluations necessary to address the primary and secondary aims. OBTAIN OTHER STUDIES AS REQUIRED FOR GOOD CLINICAL CARE.

Comments

(Include any held doses, or dose modifications)

